2 PROTOCOL ACTIVITIES BY VISIT

Study visits may be impacted due to the COVID-19 pandemic. This may include changes such as phone or virtual visits, visits at alternative locations, or changes in the visit frequency and timing of study procedures, among others. Additional details are provided in the subsequent section. Every effort should be made to ensure the safety of subjects and site staff, while maintaining the integrity of the study. If visits cannot be conducted onsite due to logistical restrictions or other pandemic-related reasons, follow the updates below on how to proceed.

COVID-19 Pandemic-Related Acceptable Protocol Modifications

During the COVID-19 pandemic, if it is not possible for all study procedures to be performed as specified due to travel restrictions or other reasons, the following modifications are allowed:

- Study visits and/or activities should be performed at the study site and as scheduled whenever possible. If a subject is unable to visit the study site due to COVID-19-related issues, the subject should perform the visit/related activities at the earliest feasible opportunity and as per the following modifications.
 - Reschedule study visits as soon as possible and contact AbbVie if out-of-window to obtain guidance on which visit should be performed once the subject's return to site has been confirmed.
 - Regardless of when the rescheduled onsite visit may occur, a phone call from the site to the enrolled subject should be conducted as close to the originally scheduled date of the study visit as possible to query for any adverse events and review concomitant medications.

2.1 Individual Treatment Period Visit Activities

This section presents a list of activities performed during each visit, organized by visit. The dot pattern on the upper right indicates the place of the visit in the overall Treatment Period Activity Schedule.

Activities are grouped by category (Interview, Exam, etc.). Further information about each activity is provided in Section 3.

SCREENING:

INTERVIEW	
 • Subject information and informed consent • Demographics • Eligibility criteria • Medical (including psoriasis)/surgical history 	
 • Drug, tobacco (including e-cigarettes), and alcohol history • AE assessment • Prior/concomitant therapy • Latent TB risk assessment form
PRO	
 • Dispense handheld ePRO device 	
 • GPSS and GenPs-SFQ for subjects with genital involvement • PSS for subjects with scalp involvement
EXAM	
 • 12-lead ECG • Height • Weight • Vital signs • Physical exam 	
 • BSA • sPGA-G and sPGA for subjects with genital involvement • Scalp IGA, PSSI, and sPGA for subjects with scalp involvement
CENTRAL LAB	
 • HIV, HBV, and HCV screening • FSH (if applicable) • Serum pregnancy test (for all female subjects of childbearing potential) 	
 • TB test (QuantiFERON-TB Gold test [or IGRA equivalent] and/or local PPD skin test) • Hematology (including CBC) • Clinical chemistry • Urinalysis

NOTES: All screening procedures must be performed onsite, with the exception of PRO assessments. GPSS and PSS will be assessed daily and GenPs-SFQ will be assessed weekly until Week 16.

Baseline/DAY 1:

INTERVIEW	
 • Eligibility criteria • Medical (including psoriasis)/surgical history 	
 • AE assessment • Prior/concomitant therapy
PRO	
 • Study-G: GPSS, GenPs-SFQ, PatGA-Genital, DLQI, HADS 	
 • Study-S: PSS, Scalp Itch NRS, DLQI, HADS
EXAM	
 • Vital signs • Physical exam • Photography (optional) 	
 • BSA • Study-G: sPGA-G, sPGA • Study-S: scalp IGA, PSSI, sPGA
LAB	
 • Urine pregnancy test (for all female subjects of childbearing potential) 	
CENTRAL LAB	
 • Hematology (including CBC) 	
 • Clinical chemistry
TREATMENT	
 • Randomization/drug assignment • Administer study drug 	
 • In-clinic post-dose monitoring for hypersensitivity reactions

NOTES: GPSS and PSS will be assessed daily and GenPs-SFQ will be assessed weekly until Week 16.

WEEK 4:

INTERVIEW	
 • AE assessment 	
 • Prior/concomitant therapy
PRO	
 • Study-G: GPSS, GenPs-SFQ, PatGA-Genital, DLQI, HADS 	
 • Study-S: PSS, Scalp Itch NRS, DLQI, HADS
EXAM	
 • Vital signs • Photography (optional) 	
 • Study-G: sPGA-G, sPGA • Study-S: scalp IGA, PSSI, sPGA
LAB	
 • Urine pregnancy test (for all female subjects of childbearing potential) 	
TREATMENT	
 • Administer study drug 	
 • In-clinic post-dose monitoring for hypersensitivity reactions

NOTES: GPSS and PSS will be assessed daily and GenPs-SFQ will be assessed weekly until Week 16.

WEEK 16:

INTERVIEW	
 • AE assessment 	
 • Prior/concomitant therapy
PRO	
 • Study-G: GPSS, GenPs-SFQ, PatGA-Genital, DLQI, HADS 	
 • Study-S: PSS, Scalp Itch NRS, DLQI, HADS • Collect handheld ePRO device
EXAM	
 • Vital signs • Photography (optional) 	
 • Study-G: sPGA-G, sPGA • Study-S: scalp IGA, PSSI, sPGA
LAB	
 • Urine pregnancy test (for all female subjects of childbearing potential) 	
TREATMENT	
 • Administer study drug 	
 • In-clinic post-dose monitoring for hypersensitivity reactions

WEEK 28:

INTERVIEW	
 • AE assessment 	
 • Prior/concomitant therapy
PRO	
 • Study-G: GPSS, GenPs-SFQ, PatGA-Genital, DLQI, HADS 	
 • Study-S: PSS, Scalp Itch NRS, DLQI, HADS
EXAM	
 • Vital signs • Photography (optional) 	
 • Study-G: sPGA-G, sPGA • Study-S: scalp IGA, PSSI, sPGA
LAB	
 • Urine pregnancy test (for all female subjects of childbearing potential) 	
CENTRAL LAB	
 • Hematology (including CBC) 	
 • Clinical chemistry
TREATMENT	
 • Administer study drug 	
 • In-clinic post-dose monitoring for hypersensitivity reactions

WEEK 40:

INTERVIEW	
 • AE assessment 	
 • Prior/concomitant therapy
PRO	
 • Study-G: GPSS, GenPs-SFQ, PatGA-Genital, DLQI, HADS 	
 • Study-S: PSS, Scalp Itch NRS, DLQI, HADS
EXAM	
 • Vital signs • Photography (optional) 	
 • Study-G: sPGA-G, sPGA • Study-S: scalp IGA, PSSI, sPGA
LAB	
 • Urine pregnancy test (for all female subjects of childbearing potential) 	
TREATMENT	
 • Administer study drug 	
 • In-clinic post-dose monitoring for hypersensitivity reactions

WEEK 52/Premature Discontinuation:

INTERVIEW	
 • AE assessment 	
 • Prior/concomitant therapy
PRO	
 • Study-G: GPSS, GenPs-SFQ, PatGA-Genital, DLQI, HADS 	
 • Study-S: PSS, Scalp Itch NRS, DLQI, HADS
EXAM	
 • Weight • Vital signs • Physical exam • Photography (optional) 	
 • Study-G: sPGA-G, sPGA • Study-S: scalp IGA, PSSI, sPGA
CENTRAL LAB	
 • Hematology (including CBC) • Clinical chemistry 	
 • TB test (QuantiFERON-TB Gold test [or IGRA equivalent] and/or local PPD skin test)

NOTES: Photography is not required for premature discontinuation. TB test is not required for premature discontinuation if less than 52 weeks since previous TB test.

2.2 Individual Post-Treatment Period Visit Activities

This section presents a list of activities performed during follow-up. The dot pattern on the upper right indicates the place of the visit/call in the overall Post-Treatment Period Activity Schedule.

Activities are grouped by category (Interview, Exam, etc.). Further information about the activities is presented in Section 3.

FOLLOW-UP PHONE CALL (20 Weeks After Last Study Drug Dose):

INTERVIEW	
 • AE assessment 	
 • Prior/concomitant therapy
-----------	---	---

NOTES: Does not apply to subjects who initiate commercial risankizumab or continue in the optional CTE.

2.3 Optional Continuous Treatment Extension (CTE)

This section presents a list of activities performed during the optional CTE, organized by visit. The dot pattern on the upper right indicates the place of the visit in the overall CTE.

Activities are grouped by category (Interview, Exam, etc.). Further information about the activities is presented in Section 3.

WEEK 52 AND EVERY 12 WEEKS:

 INTERVIEW	
 • Subject information and informed consent (Week 52 only) • AE assessment 	
 • Concomitant medication
 LAB	
 • Urine pregnancy test (for all female subjects of childbearing potential) 	
 TREATMENT	
 • Administer study drug 	
 • In-clinic post-dose monitoring for hypersensitivity reactions

NOTES: At Week 52, these activities will be performed in addition to the Week 52 activities in Section 2.1. At Week 52, subjects will be administered open-label risankizumab to begin CTE. Subjects will be evaluated per standard of care.

CTE WITHDRAWAL:

 INTERVIEW	
 • AE assessment 	
 • Concomitant medication
 LAB	
 • Urine pregnancy test (for all female subjects of childbearing potential) 	

NOTES: If a subject discontinues treatment with risankizumab, the withdrawal visit should be completed and the subject will automatically discontinue CTE participation.

FOLLOW-UP PHONE CALL (20 Weeks After Last Study Drug Dose):

 INTERVIEW	
 • AE assessment 	
 • Concomitant medication
---	---	--

NOTES: Does not apply to subjects who initiate commercial risankizumab or transitions to CTP OLE study.

3 STUDY PROCEDURES

3.1 Study Subject Information and Informed Consent

The investigator or their representative will explain the nature of the study to the subject, the benefits and risks anticipated from participation in the study and answer all questions regarding this study. Prior to any study-related screening procedures being performed on the subject or any medications being discontinued by the subject to participate in this study, the informed consent statement will be reviewed, signed, and dated by the subject or their legally authorized representative, the person who administered the informed consent, and any other signatories according to local requirements. A copy of the signed informed consent will be given to the subject and the original will be placed in the subject's medical record. An entry must also be made in the subject's dated source documents to confirm that informed consent was obtained prior to any study-related procedures and that the subject received a signed copy.

Information regarding benefits for subjects and information regarding provisions for treating and/or compensating subjects who are harmed because of participation in the study can be found in the informed consent form.

Optional photography will only be performed if the subject has voluntarily signed and dated a separate written consent form for photography that has been approved by an IRB/IEC, after the nature of the photography has been explained and the subject has had an opportunity to ask questions. The separate written consent may be part of the main consent form. If the subject does not consent to the photography, it will not impact the subject's participation in the study.

Due to the COVID-19 pandemic, it is possible that additional protocol modifications not outlined in this protocol may become necessary. If this situation arises, in addition to the study informed consent, additional verbal consent may be obtained prior to these adaptations or substantial changes in study conduct in accordance with local regulations. An appropriately signed and dated informed consent form should be obtained from the subject afterwards, as soon as possible.

3.2 Medical History

A complete medical and surgical history including demographics, history of hepatitis B vaccination, TB screening, tobacco, alcohol, and drug use will be taken at screening. The subject's medical and surgical history will be updated at the Study Baseline/Day 1 visit. This updated medical history will serve as the baseline for clinical assessments.

Subjects should have no history of clinically significant (per investigator's judgment) drug or alcohol abuse within the last 6 months.

3.3 Adverse Event Assessment

Please refer to Section [4.1](#).

3.4 Patient-Reported Outcomes

Subjects will complete the self-administered PRO instruments (when allowed per local regulatory guidelines). Subjects should be instructed to follow the instructions provided with the instrument and to provide the best possible response to each item. Site personnel shall not provide interpretation or assistance to subjects other than encouragement to complete the tasks. Subjects who are functionally unable to read any of the instruments may have site personnel read the questionnaire to them. Site personnel will encourage completion of the instrument at all specified visits and will ensure that a response is entered for all items.

PRO instruments that are administered at the site should be completed at the specified study visit prior to clinical assessments, dosing, or any other procedure and prior to any discussion of adverse events or any review of laboratory findings. The subject should complete the questionnaire before site personnel perform any clinical assessments and before any interaction with site personnel has occurred to avoid biasing the subject's response.

The following PRO assessments that are required between site visits will be collected electronically from subjects in the evening using a handheld ePRO device provided to the subject at Screening:

- GPSS and PSS will be collected DAILY starting at Screening until Week 16.
- GenPs-SFQ will be collected WEEKLY starting at Screening until Week 16.

At the visits specified in Section 2.1, all PRO assessments will be collected electronically at the site using an electronic device supplied by AbbVie. The device will be programmed to allow data entry for only the visits specified in the protocol and will not allow subjects to complete more than one of the same assessments at one visit.

All data entered on the handheld and electronic tablet devices will be immediately stored to the devices themselves and automatically uploaded to a central server.

The PRO instruments are described as follows.

All Subjects

- Dermatology Life Quality Index (DLQI): The DLQI is a self-administered, 10-question questionnaire covering 6 domains (symptoms and feelings, daily activities, leisure, work and school, personal relationships, treatment) and has a 1-week recall period. The response options range from 0 (not affected at all) to 3 (very much affected). This gives an overall range of 0 to 30 where lower scores mean better quality of life.
- Hospital Anxiety and Depression Scale (HADS): The HADs is a self-assessment scale which detects the presence and severity of anxiety and depression in the general population. It contains 14 items and is comprised of anxiety (7 items) and depression (7 items) subscales, which are scored separately and summed to give a total score. Item scores range from 0 (best) to 3 (worst) and total scores are categorized as normal (0 – 7), borderline abnormal (8 – 10) and abnormal (11 – 21). The HADs has been widely used in clinical trials in a variety of disease areas and has extensive evidence to support its acceptability, reliability and validity.

Study-G

- Genital Psoriasis Symptoms Scale (GPSS):** The GPSS is a patient-administered assessment of 8 symptoms: itch, pain, discomfort, stinging, burning, redness, scaling, and cracking. Respondents are asked to answer the questions based on their psoriasis symptoms in the genital area. Genital area is defined as the labia majora (outer lip), labia minora (inner lip), and perineum (area between vagina and anus) for females; penis, scrotum, and perineum (area between the penis and anus) for males. The self-reported overall severity of each of the 8 symptoms individually in the genital area is assessed on an 11-point horizontal NRS anchored at 0 (no) and 10 (worst imaginable), using a recall period of 1 day.
- Genital Psoriasis Sexual Frequency Questionnaire (GenPs-SFQ):** The GenPs-SFQ is a PRO measure to evaluate the impact of genital psoriasis symptoms on sexual frequency, using a 1-week recall period. It consists of 2 items that assess the impact of genital psoriasis symptoms on the frequency of sexual activity. Each item uses a Likert scale. Respondents are asked to answer the questions based on their psoriasis symptoms in the genital area. Genital area is defined as the labia majora (outer lip), labia minora (inner lip), and perineum (area between vagina and anus) for females; penis, scrotum, and perineum (area between the penis and anus) for males. The definition of sexual activity is not limited to intercourse and includes activities such as masturbation.

Item 1 asks how many times a patient engaged in sexual activity in the past week with response options of none/zero (2), once (1), and two or more (0). Item 2 assesses how often genital psoriasis symptoms limited the frequency of sexual activity with response options ranging from 0 (never) to 4 (always). The individual item scores of the SFQ are reported separately. No total score is calculated for SFQ. The instructions for completion are embedded within the SFQ questionnaire for patients to read before responding to items. SFQ individual item scores at Week 16 are the scores collected at Week 16 on site.
- Patient's Global Assessment of Genital Psoriasis (PatGA-Genital):** The PatGA-Genital is a patient-administered, single-item scale on which patients are asked to rank, by circling a number on a 0 to 5 NRS, the severity of their genital psoriasis "today" from 0 (clear), no genital psoriasis; to 5 (severe).

Study-S

- Psoriasis Symptoms Scale (PSS):** The PSS is a 4-item PRO instrument that assesses the severity of psoriasis symptoms in patients with moderate to severe psoriasis, using a recall period of 1 day. The symptoms include pain, redness, itching and burning from psoriasis. Current symptom severity is assessed using a 5-point Likert-type scale ranging from 0 (none) to 4 (very severe). Until Week 16, the weekly average score is calculated based on the 7 available daily scores from the days within each visit window that were closest to the nominal. The PSS was developed based on published evidence supporting the development of two similar, proprietary PRO instruments: the Psoriasis Symptom Inventory and the Psoriasis Symptom Diary.
- Scalp Psoriasis Itch Numeric Rating Scale (Scalp Itch NRS):** The Scalp Itch NRS is a self-administered NRS that asks the patients to assess their scalp itch on a scale from 0 to 10 where 0 represents no itch and 10 represents worst imaginable itch. Scalp Itch NRS has been used in previous trials assessing the efficacy of apremilast among patients with scalp psoriasis.¹

3.5 Efficacy Assessments

Most efficacy assessments will be recorded on paper worksheets and entered into the eCRF (sPGA-G and scalp IGA will be collected electronically). Efficacy assessments will be conducted at the study visits specified in the protocol. To minimize variability, the same assessor should evaluate the subject at each visit for the duration of the trial. A back-up assessor should be identified. The assessor must be a qualified medical professional (e.g., nurse, physician's assistant, or physician). Any assessor must have completed training for skin assessments (sPGA-G, scalp IGA, and BSA) as detailed by the sponsor, and be competent in performing such assessments. It is the responsibility of the site investigator to ensure that all assessors are qualified and trained to perform assessments and that all training is documented. If the assessor is not available, the pre-identified back-up assessor should perform such assessments.

All Subjects

- **Body Surface Area (BSA) – Psoriasis:** The subject's right or left hand should be selected as the measuring device. For purposes of clinical estimation, the total surface of the palm plus five digits will be assumed to be approximately equivalent to 1%. Measurement of the total area of involvement by the physician is aided by imagining if scattered plaques were moved so that they were next to each other and then estimating the total area involved.
- **Static Physician Global Assessment (sPGA):** This sPGA is a 5-point score ranging from 0 to 4 (where 0 = clear), based on the physician's assessment of the average thickness, erythema, and scaling of all psoriatic lesions. The assessment is considered "static" which refers to the patient's disease state at the time of the assessments, without comparison to any of the patient's previous disease states, whether at Baseline or at a previous visit.

Study-G

- **Static Physician Global Assessment of Genitalia (sPGA-G):** The sPGA-G is a 5-point score ranging from 0 to 4, based on the physician's assessment of the average thickness, erythema, and scaling of all psoriatic lesions. The assessment is considered "static" which refers to the patient's disease state at the time of the assessments, without comparison to any of the patient's previous disease states, whether at Baseline or at a previous visit.

Study-S

- **Scalp Investigator Global Assessment (scalp IGA):** The scalp IGA is a measurement of overall scalp involvement by the investigator at the time of evaluation. The scalp IGA is a 5-point scale ranging from 0 (clear) to 4 (severe) incorporating an assessment of the severity of the 3 primary signs of the disease: erythema, scaling, and plaque elevation. When making the assessment of overall scalp severity, the investigator should factor in areas that have already been cleared (i.e., have scores of 0) and not just evaluate remaining lesions for severity, i.e., the severity of each sign is averaged across all areas of involvement, including cleared lesions.
- **Psoriasis Scalp Severity Index (PSSI):** The physician will assess the severity of scalp psoriasis using the PSSI, which consists of an assessment of erythema, induration, and desquamation on a scale from 0 (none) to 4 (very severe) and the percentage of scalp involved on a scale from 0 (< 10%

of scalp involved) to 6 (90 to 100% of scalp involved). The composite score is calculated as the sum of the scores for erythema, induration and desquamation multiplied by the score recorded for the extent of scalp area involved. The PSSI ranges from 0 to 72. A negative change from baseline indicates improvement.

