7.1 Demographics and Baseline Characteristics

Demographics and baseline disease characteristics will be summarized descriptively, overall and by treatment group for the ITT Populations. Unless otherwise specified, baseline is defined as the last non-missing value prior to the first administration of study treatment (or randomization date if no study treatment was administered).

Continuous demographic variables include age, weight, height, and body mass index (BMI).

Categorical demographic variables include: sex, ethnicity (Hispanic or Latino, Not Hispanic or Latino), race, Age (< 40, ≥ 40 to < 65, ≥ 65 years), weight (≤ 100 kg, > 100 kg), BMI (normal: < 25; overweight: ≥ 25 to < 30; obese: ≥ 30 kg/m²), Nicotine user (current, former, never, unknown), alcohol user (current, former, never, unknown).

Baseline disease characteristics include BSA (< 10%, ≥ 10%), prior biologic therapies for psoriasis (0, ≥ 1), sPGA (3,4), sPGA-G (3,4) for Study-G only, scalp IGA (3,4) for Study-S only, PSSI (by median) for Study-S only.

Patient Reported Outcomes (PROs) analyzed at baseline include:

- Study-G: GPSS, GenPs-SFQ, PatGA-Genital, DLQI (Dermatology Life Quality Index), and HADS
- Study-S: PSS, Scalp Itch NRS (Numerical Rating Scale), DLQI, and HADS

In addition to the analysis of Itch NRS as a continuous variable, Itch NRS ≥ 4 will be summarized as a categorical baseline variable.

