11.2.1 Static Physician Global Assessment of Genitalia (sPGA-G)

The sPGA-G is a 6-point score ranging from 0 to 5. The sPGA-G score should be selected using the descriptors below that best describe the overall appearance of the subject's psoriasis lesions in genital area at a given time point. It is not necessary that all three criteria be fulfilled. The sPGA of Genitalia score should be based on a combination of erythema and the secondary features (plaque elevation and/or scale). Since erythema is the most robust finding, it should be the dominant feature influencing the sPGA of Genitalia rating in the majority of cases.

Score	Category	Category Description
0	Clear	Erythema = 0 (residual post-inflammatory hyperpigmentation or hypopigmentation may be present) Plaque elevation = 0 (no elevation over normal skin) Scaling = 0 (no scale)
1	Minimal	Erythema = faint (light pink coloration) Plaque elevation = \pm (possible but difficult to ascertain whether there is a slight elevation above normal skin) Scaling = \pm (surface dryness with some white coloration)
2	Mild	Erythema = mild (pink to light red coloration) Plaque elevation = slight (slight but definite elevation, typically edges are indistinct or sloped) Scaling = fine (fine scale partially or mostly covering lesions)
3	Moderate	Erythema = moderate (definite red coloration) Plaque elevation = moderate (moderate elevation with rough or sloped edges) Scaling = coarser (coarse scale covering most of all of the lesions)
4	Severe	Erythema = severe (bright red coloration) Plaque elevation = marked (marked elevation typically with hard or sharp edges) Scaling = coarse (coarse, non-tenacious scale predominates covering most or all of the lesions)
5	Very Severe	Erythema = very severe (extreme red coloration; dusky to deep red coloration) Plaque elevation = very marked (very marked elevation typically with hard sharp edges) Scaling = very coarse (coarse, thick tenacious scale over most of all of the lesions; rough surface)

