14.0 Version History

Table 3. SAP Version History Summary

Version	Date	Summary
1.0	04 October 2023	Initial version
2.0	01 November 2024	Updated to incorporate agency feedback, including: 
 Specify the analysis method for categorical variables in Section 9.1 Add sensitivity analysis: MI and tipping points for primary endpoints in Section 9.3.3 Update subgroup analysis in Section 9.6 Add scale description of Patient-Reported Outcome and Physician-Assessed Endpoints in Section 11.0 Add some details regarding the final list of ASI in Section 10.2.6 for clarification purpose Clarify MMRM method for continuous variable in Section 9.1
3.0	07 February 2025	
 In the subgroup analysis of sPGA-G 0/1 in Section 9.6, updated the Baseline sPGA-G (3, 4) subgroup to (3, ≥ 4), which is an error in the protocol. In Section 7.2, deleted the sentence 'In addition, a subject's prior biologic use will be summarized by the reason for discontinuation' because the corresponding CRF page was not collected. Clarified the Period B exposure duration definition in Section 6.0 and ALL RZB TEAE definition in Section 10.2.1.
4.0	18 February 2025	
 In Section 11.2.4, the scale of percentage of scalp involved is updated to 1 – 6 from 0 – 6 according to protocol admin change.

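### The sPGA-G is a 0–4 score in the Operations Manual and a 0–5 score in the SAP, and SAP 7.1 has no category for a baseline score of 5

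*Protocol*

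**What the plan says.** **Operations Manual (Protocol Appendix G), Section 3.5.** "The sPGA-G is a 5-point score ranging from 0 to 4". The rating rests on the "average thickness, erythema, and scaling of all psoriatic lesions". Apart from the name of the scale and a note on what 0 means, this repeats the overall sPGA entry just above it. There are no category descriptors, and the sentence does not limit the rating to genital lesions. The same section adds that "sPGA-G and scalp IGA will be collected electronically" and that assessors complete sponsor training. Neither the form nor the training material is among the documents.

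**SAP 11.2.1.** "The sPGA-G is a 6-point score ranging from 0 to 5". The rating is of lesions in the genital area, by the best-fitting of six described categories, the highest being Very Severe (5). "It is not necessary that all three criteria be fulfilled". On erythema, the SAP says "it should be the dominant feature influencing the sPGA of Genitalia rating in the majority of cases".

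**Baseline categories.** Protocol 7.4 lists the subgroup as 3 and 4. SAP 9.6 lists it as 3 and ≥ 4. The version 3.0 entry in SAP 14.0 says that it "updated the Baseline sPGA-G (3, 4) subgroup to (3, ≥ 4), which is an error in the protocol", and SAP 14.1 repeats the subgroup change. SAP 7.1 still lists "sPGA-G (3,4) for Study-G only".

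**Use of the scale.** Entry to Study-G needs a score of at least 3 at Screening and Baseline (Protocol 5.1, criterion 6). The primary endpoint is a score of 0 or 1 at Week 16 (Protocol 3.2) and the first ranked secondary is a score of 0 (Protocol 3.3).

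**The concern.** One instrument decides who enters Study-G and whether each subject counts as a responder, and the current texts give it two ranges that cannot both be right. The SAP evidently works on 0–5, since a category of ≥ 4 serves no purpose on a scale that stops at 4. The reconciliation nevertheless stopped at a single subgroup. The supplied Operations Manual keeps the shorter range and the wider lesion scope, SAP 14.1 lists neither as a difference, and SAP 7.1 keeps the categories that the SAP itself calls an error.

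Two things are at stake. A baseline table programmed as SAP 7.1 is written can leave eligible subjects out of its rows and disagree with the subgroup table on the same variable. And a reader of the results cannot tell from the documents which description the assessors worked from.

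**Working it through.** **1. The plan's own figure for this endpoint.** Protocol 7.8 assumes 13% response on placebo, a difference of 53 points (so 66% on risankizumab), 50 subjects per arm and a two-sided 0.05 chi-square test, and states power above 90%.

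- Pooled rate: (0.13 + 0.66)/2 = 0.395
- Standard error under the null: √(2 × 0.395 × 0.605/50) = 0.0978
- Standard error under the alternative: √((0.13 × 0.87 + 0.66 × 0.34)/50) = 0.0822
- z = (0.53 − 1.96 × 0.0978)/0.0822 ≈ 4.12, so power ≈ 99.998%

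The stated figure is reproduced. It takes the endpoint as given and does not depend on where the top of the scale lies.

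**2. Which scores each rule admits.**

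| Rule | On 0–4 | On 0–5 |
|---|---|---|
| Entry, score ≥ 3 | 3, 4 | 3, 4, 5 |
| Primary responder | 0, 1 | 0, 1 |
| First ranked secondary responder | 0 | 0 |
| Primary non-responder | 2, 3, 4 | 2, 3, 4, 5 |
| Covered by SAP 7.1 categories | 3, 4 | 3, 4 (5 left out) |
| Covered by SAP 9.6 categories | 3, 4 | 3, 4, 5 |

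The responder sets and the entry threshold are numerically the same on both scales. The extra score adds one value at the severe end, which is eligible at baseline and a non-response at Week 16. The range alone does not move the endpoint.

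**3. The gap in SAP 7.1.** If k of about 100 Study-G subjects have a baseline score of 5, the two rows in SAP 7.1 add up to 100 − k, while the SAP 9.6 subgroups add up to 100. The documents give no value for k, which may be zero.

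**4. Lesion scope.** The Operations Manual sentence refers to psoriatic lesions in general; the SAP refers to the genital area. The name of the scale supplies the genital scope, so this looks like wording carried over from the overall sPGA rather than a different measurement. It still needs correcting.

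**5. Rating description.** Both texts rate the same three signs: thickness or elevation, erythema and scaling. The Operations Manual speaks of an average and says nothing of a dominant sign. The SAP uses a best-fitting descriptor with erythema leading in most cases. The Operations Manual sentence can be read in two ways:

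- The three signs are averaged into one score. That would sit badly with erythema dominance.
- Each sign is averaged across lesions. The scalp IGA entry in the same section of the Operations Manual uses averaging in this sense. On this reading no rule for combining the signs is stated, and nothing contradicts the SAP.

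The text does not settle which is meant. The descriptions differ in detail, but a contradiction is not established.

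**The case against.** The strongest reply is that a one-sentence summary is being set against the full instrument text. The Operations Manual gives no descriptors, so it can hardly have been the assessors' working tool; the electronic form and training were. They may have used the 0–5 version throughout. SAP 14.0 also cites, for a different scale, a protocol administrative change that is not in the supplied text, so a similar correction for the sPGA-G cannot be ruled out. Period A is double-blind with syringes of identical appearance, and the same assessor should rate a subject at every visit, so whichever description was used should apply to both arms. The subgroup change from Protocol 7.4 is openly disclosed and is not itself an error.

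Most of this stands. It limits the point to what the supplied text shows and gives no ground for alleging bias between arms. It does not remove the two ranges, and it does not touch SAP 7.1, which conflicts with Sections 9.6 and 11.2.1 of the same document.

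A reader might go further and infer that the two rating rules contradict each other and would move borderline subjects across the 0/1 cut. The documents do not support that. Neither states a formula for combining the signs, and the Operations Manual sentence has a reading that is compatible with the SAP. Any count of subjects who would change status would rest on weights and rounding that appear in neither document.

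**Conclusion.** The point holds as an internal inconsistency: wrong as written, and between a minor correction and a low-priority should-fix. Two faults are certain from the current text. The range of the sPGA-G is 0–4 in one document and 0–5 in the other, and SAP 7.1 has no category for a baseline score that SAP 11.2.1 and the entry rule allow. The demonstrated consequence is confined to one descriptive baseline table and to uncertainty about which description produced the data.

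It would be tempting to conclude that the Study-G primary result or its power is in doubt. Nothing supports that. The cut-points (≥ 3, 0/1 and 0) are the same in both documents, power on the stated assumptions is far above 90%, and no effect on response rates is shown. Nor do the documents show that anyone was rated on the wrong scale.

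What remains open is which version is on the electronic form and in the training, whether more than one was used, and how many subjects scored 5 at baseline.

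**What to change.** 1. Change the baseline sPGA-G categories in SAP 7.1 to (3, ≥ 4), to match SAP 9.6. This is safe on either scale: if the maximum is 4, the upper category simply contains the 4s.
2. Confirm which version of the sPGA-G is on the electronic form and in assessor training. Then reconcile Operations Manual 3.5 with SAP 11.2.1 on range, genital scope and rating description, correcting SAP 11.2.1 too if it is not the version in use.
3. State in the SAP which version produced the data. If both were in use at different times or sites, report the number of subjects rated under each, by arm.

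The cost is a few lines of text, one table category and one check of the form and training material. No threshold, test or sample size changes. Counts by arm are needed only if two versions turn out to have been used.
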